19.5 Incentives to Patients

Not applicable.

ANNEX 1: Study Drug Label Information

ANNEX 2: Signature pages for Principal Investigators

ANNEX 3: Common Terminology Criteria for Adverse Events (CTCAE) Version 4.03,
U.S. DEPARTMENT OF HEALTH AND HUMAN SERVICES National Institutes of
Health National Cancer Institute, Publish Date: June 14, 2010.

ANNEX 4: Length of Stay calculation Worksheet

ANNEX 5: Product Information for INTRALIPID 20% (a 20% intravenous fat emulsion),
revised May 2015.

Categorization of Z-Scores on Fenton and WHO Growth Charts.....	37

Statistical Analysis Plan

FK Study Identifier: SMOF-018-CP3

List of abbreviations and definition of terms

Abbreviation	Definition
AE	Adverse event
AUC	Area under the curve
ALT	Alanine aminotransferase
ALP	Alkaline phosphatase
AST	Aspartate aminotransferase
ATC	Anatomical Therapeutic Chemical Classification System
BDRM	Blinded Data Review Meeting
BUN	Blood urea nitrogen
CRF	Case report form
CRP	C-reactive protein
CS	Clinically significant
CTM	Clinical trial material
DSMB	Data safety monitoring board
FDA	Food and Drug Administration
GCP	Good Clinical Practice
GGT	Gamma-glutamyl transferase
GMP	Good Manufacturing Practice
HEENT	Head, eyes, ears, nose, and throat

Version (of CSP): 3.0

CONFIDENTIAL

page 7 of 56

date: 5 OCT 2020

Annex No.: **██████████**
Document No.: **██████████**

00
1

Date:
Page:

██████████
7 of 56

Statistical Analysis Plan

FK Study Identifier: SMOF-018-CP3

Abbreviation	Definition
ICH	International Council for Harmonisation of Technical Requirements for Pharmaceuticals for Human Use
IWRS	Interactive web response system
MedDRA	Medical Dictionary for Regulatory Activities
MGRS	Multicenter growth reference study
n	Number
NCS	not clinically significant
NEC	Necrotizing enterocolitis
PARP	Product accountability and randomization plan
PN	Parenteral nutrition
SAE	Serious adverse event
SAP	Statistical analysis plan
TEAE	Treatment-emergent adverse event
TG	Triglycerides
WHO	World Health Organization

Statistical Analysis Plan

FK Study Identifier: SMOF-018-CP3

1 INTRODUCTION

This Statistical Analysis Plan (SAP) describes the statistical methods and data presentations to be used in the summary and analysis of safety, and efficacy data from Protocol SMOF-018-CP3. This document reflects the amendments to the protocol and changes in statistical analysis after the interim analysis and consultancy with the Food and Drug Administration (FDA). Background information is provided for the overall study design and objectives. For details on study designs and data collection, the reader is referred to the study protocol, the interim analysis plan, the product accountability and randomization plan, and the case report form (CRF).

The content of this document and the Interim Analysis Plan are compliant with International Council for Harmonisation (ICH) guideline E9 - Statistical Principles for Clinical Trials. Any text copied from the study protocol has been italicized.

Version (of CSP): 3.0

CONFIDENTIAL

page 9 of 56

date: 5 OCT 2020

████████████████████
Annex No.: 1
Document No.: ██████████

00
1

Date:
Page:

████████████████████
9 of 56

Statistical Analysis Plan

FK Study Identifier: SMOF-018-CP3

2 MODIFICATION HISTORY

2.1 Changes to the study protocol

This SAP reflects the amendments to the study protocol and changes in statistical analysis after the interim analysis and consultancy with the FDA.

2.2 Changes to previous SAP versions

This is version 2.0 of the SAP for the final analysis.

It is based on the following documents:

- Study Protocol SMOF-018-CP3 CSP final (Version 3.0, 5-October-2020)
- Statistical analysis plan (Version 1.0, 14-July-2015)
- Interim Analysis Plan Version 1.0, (14-February-2019)
- Product Accountability and Randomization Plan (Version 1.2, 31-March-2016)
- Case Report forms (e CRF, 26-July-2018)

The following major changes were included compared to SAP version 1.0:

Version	Date	Changes
2.0	29-Oct--2020	
Chapter 2: Modification history added
 
Chapter 3: Primary objective changed from confirmatory to exploratory
 
Chapter 4: Condensed description of study design and procedures Requirement for figures in BDRM deleted Reference to BDRM on 28-Oct-2020 included
 
Chapter 5: “Cumulative number of days of conjugated bilirubin levels > 1.5 mg/dL in patients” deleted from list of safety variables per study protocol Version 3.0

Version (of CSP): 3.0

CONFIDENTIAL

page 10 of 56

date: 5 OCT 2020

Annex No.: [REDACTED]
Document No.: [REDACTED]

00
1

Date:
Page:

[REDACTED]
10 of 56

Statistical Analysis Plan

FK Study Identifier: SMOF-018-CP3

	
Chapter 7:
 
Statistical considerations adapted to changes in study design after interim analysis.
 
Study week defined
 
Details on imputation of missing data added, imputation of primary endpoint changed to “primary endpoint not met” if all post-baseline assessments missing (scenario C).

	
Chapter 8:
 
Presentation of protocol deviations according to CRF categories
 
Presentation of medical history according to CRF categories instead of MedDRA codes
 
Summary of prior and concomitant medication by ATC levels 2 and 4 instead of level 1 and preferred term
 
Change of primary analysis from confirmatory to descriptive and exploratory analysis
 
Line plot of mean Z-values replaced by box plot
 
Cumulative risk analysis of time to enteral or oral feed amended
 
Number of events added to AE summary tables
 
AE summary tables by relationship and severity added
 
Summary of TEAEs occurring with an incidence > 5% added
 
Analysis of AEs of special interest in the following categories added:
 
• all major neonatal morbidities• bronchopulmonary dysplasia• retinopathy of prematurity• intraventricular hemorrhage• periventricular leukomalacia• necrotizing enterocolitis• late-onset sepsis in premature and low birth weight neonates

Version (of CSP): 3.0

CONFIDENTIAL

page 11 of 56

date: 5 OCT 2020

Annex No.: [REDACTED]
Document No.: [REDACTED]

00
1

Date:
Page:

[REDACTED]
11 of 56

Statistical Analysis Plan

FK Study Identifier: SMOF-018-CP3

		Additional AE tables for subgroups analysis by race and ethnicity added Cumulative risk analysis of discharge from hospital amended Analysis of caloric target removed as data not collected
--	--	--

Version (of CSP): 3.0

CONFIDENTIAL

page 12 of 56

date: 5 OCT 2020

████████████████████
Annex No.:
Document No.:

00
1
████████████████████

Date:
Page:

████████████████████
12 of 56

Statistical Analysis Plan

FK Study Identifier: SMOF-018-CP3

3 STUDY OBJECTIVES

3.1 Primary Objective(s)

The primary objective of the study is to compare the safety of Smoflipid and Intralipid as measured by the number of study patients in each treatment group with conjugated bilirubin >2 mg/dL during the first 28 days of study treatment, confirmed by a second sample collected 7 days after the first sample.

3.2 Secondary Objective(s)

The secondary objectives are to

- compare efficacy of Smoflipid 20% to Intralipid 20% in neonates and infants reflected by specific nutritional endpoints
- evaluate overall safety of Smoflipid 20% in neonates

Statistical Analysis Plan

FK Study Identifier: SMOF-018-CP3

4 STUDY DESIGN

Number of centers: 15 (US)

Randomized: Yes

Blinded: Double-blind

Design: Parallel two-stage group-sequential adaptive design,
with interim analysis and sample size adjustment after stage 1

Dosing: Target maximal lipid dose is 3.0 g/kg/day

Placebo controlled: No

Strata: Underlying Disease -
(1) No Necrotizing Enterocolitis (No NEC)
(2) NEC

Treatments: A: Smoflipid
B: Intralipid

Version (of CSP): 3.0

CONFIDENTIAL

page 14 of 56

date: 5 OCT 2020

██████████

00

Date:

██████████

Annex No.:

1

Page:

14 of 56

Document No.:

██████████

Statistical Analysis Plan

FK Study Identifier: SMOF-018-CP3

4.1 Study Schedule

The schedule and sequence of procedures and assessments at screening, baseline, during treatment, the treatment extension phase and at the follow-up visit are summarized in the study schedule table shown below. Details of procedures and assessments are given in the Study Protocol.

Version (of CSP): 3.0

CONFIDENTIAL

page 15 of 56

date: 5 OCT 2020

████████████████████
Annex No.: 1
Document No.: ██████████

00
1

Date:
Page:

████████████████████
15 of 56

Statistical Analysis Plan

FK Study Identifier: SMOF-018-CP3

Study Schedule

Initial Treatment Phase							Treatment Extension Phase							Follow-up Visit	
Assessment / Records	Screening	Day 1 Baseline	Day 8	Day 15	Day 22	Day 29 / End of Treatment ^a	Day 36	Day 43	Day 50	Day 57	Day 64	Day 71	Day 78	Day 85 / End of Treatment ^a	7d after End of Treatment
Time Window (d)	Day 1 - 3d	0	±1	±1	±1	+1	±2	±2	±2	±2	±2	±2	±2	+1	±1
Parent Informed Consent	X														
In- / Exclusion Criteria	X	X													
Randomization		X													
Demographics incl. race and ethnicity	X														

Version (of CSP): 3.0

CONFIDENTIAL

page 16 of 56

date: 5 OCT 2020

Annex No.:
Document No.:

00
1

Date:
Page:

16 of 56

Statistical Analysis Plan

FK Study Identifier: SMOF-018-CP3

Initial Treatment Phase							Treatment Extension Phase							Follow-up Visit	
Assessment / Records	Screening	Day 1 Baseline	Day 8	Day 15	Day 22	Day 29 / End of Treatment ^a	Day 36	Day 43	Day 50	Day 57	Day 64	Day 71	Day 78	Day 85 / End of Treatment ^a	7d after End of Treatment
Medical History	X														
Prior Medication	X														
Physical Examination	X	X	X	X	X	X	X	X	X	X	X	X	X	X	X
Vital Signs	X	X	X	X	X	X	X	X	X	X	X	X	X	X	X
Body Length		X	X	X	X	X	X	X	X	X	X	X	X	X	X
Head Circumference		X	X	X	X	X	X	X	X	X	X	X	X	X	X
Time to Full Enteral or Oral Feeds						X								X	

Version (of CSP): 3.0

CONFIDENTIAL

page 17 of 56

date: 5 OCT 2020

Annex No.:
Document No.:

00
1

Date:
Page:

17 of 56

Statistical Analysis Plan

FK Study Identifier: SMOF-018-CP3

Initial Treatment Phase							Treatment Extension Phase							Follow-up Visit	
Assessment / Records	Screening	Day 1 Baseline	Day 8	Day 15	Day 22	Day 29 / End of Treatment ^a	Day 36	Day 43	Day 50	Day 57	Day 64	Day 71	Day 78	Day 85 / End of Treatment ^a	7d after End of Treatment
Length of Stay															X
Blood Sampling for Conjugated Bilirubin ^b	X		X	X	X	X		X		X		X		X	(X) ^c
Blood Sampling for Biochemistry, Hematology and Coagulation ^d	X		X	X	X	X		X		X		X		X	
Blood Sample for special analyses ^e		X				X				X				X	

^a: End of treatment visit to be performed on the following day after receiving the last dose of study medication

Version (of CSP): 3.0

CONFIDENTIAL

page 18 of 56

date: 5 OCT 2020

Annex No.:
Document No.:

00
1

Date:
Page:

18 of 56

Statistical Analysis Plan

FK Study Identifier: SMOF-018-CP3

^b: If conjugated bilirubin exceeds 1.5 mg /dL it has to be assessed weekly, also after d29

^c: If conjugated bilirubin is > 1.5 mg/dL at the end of treatment visit a blood sample for the assessment of conjugated bilirubin has to be drawn at the Follow-up Visit

^d: Additional blood samples for assessment of triglycerides (TGs) and blood glucose need to be drawn during ramp up of lipid dose. Should TGs exceed 250 mg/dL at any time, lipids will be withheld until analysis of TGs in another blood sample the following morning.

^e: Special analyses: Fatty acids, sterols, α -Tocopherol

Version (of CSP): 3.0

CONFIDENTIAL

page 19 of 56

date: 5 OCT 2020

Annex No.:
Document No.:

00
1

Date:
Page:

19 of 56

4.2 Method of Assigning Patients to Treatment Groups/Randomization

Patients were identified using a sequential numbering system which combines a four-digit site number and a three-digit individual patient according to the sequence of entry into the study.

Patients were to be randomized at baseline in a 1:1 allocation ratio to receive either Smoflipid or Intralipid. Randomization was stratified according to underlying disease (Necrotizing Enterocolitis (NEC), and No NEC) and study site.

Randomization was implemented using TEMPO™ interactive web response system (IWRS). Random block sizes were used. Within each block, the number of patients allocated to each of the treatment groups was to be equal. The assigned treatment code was stored in TEMPO™.

Further details are described in the Study Protocol and the Product Accountability and Randomization Plan (PARP Version 1.2, March 31, 2016).

4.3 Blinding

As this is a double-blind study, the allocation to the treatment groups is blinded and will not be known by the Investigator, patient/ relatives, or members of the Fresenius Kabi Clinical Research Department until completion of the study. Blinded bags of study medication were dispensed to the blinded site personnel to preserve the blind for investigator and study patient. Each bag was labelled with a randomly assigned bag ID numbers from 00001 to 25000 to ensure that numbers are not indicative of study treatment. Emergency patient unblinding is also managed in TEMPO™.

4.4 Determination of Sample Size

Due to the lack of reliable data on the effect size of Smoflipid compared to Intralipid a two-stage group-sequential adaptive design according to Bauer and Köhne (Bauer, et al. 1994) was planned with an interim analysis after 100 patients (50 patients per treatment arm in the per protocol set) completed the first 28 days of study treatment (see Study Protocol and the Interim Analysis Plan for details). Based on the interim results, the study was to be stopped at interim or to be continued after sample size re-estimation.

A maximum study size of up to 200 patients per group appeared to be feasible for the scheduled recruitment period, based on recruitment estimates from the participating sites.

Statistical Analysis Plan

FK Study Identifier: SMOF-018-CP3

4.5 Null and Alternative Hypotheses

It was decided after the interim analysis and consultancy with the FDA to terminate the study and to evaluate all data descriptively and in an exploratory way. Point estimates of differences between treatment groups and corresponding two-sided 95%-confidence intervals will be presented for the primary and key secondary efficacy endpoints. Statistical hypotheses will not be tested and p-values will not be reported.

4.6 Blinded Review / Final Statistical Analysis Plan

The Sponsor will convene a Blinded Data Review Meeting (BDRM) after the data have been cleaned and before the study is unblinded. The review will be performed within the framework of the requirements of ICH E9.

The terms of reference of the BDRM shall include, but not be limited to:

- the determination of whether protocol deviations are 'major' or 'minor'.
- the allocation of patients to analysis sets
- a review of missing data and outliers, their assessment and definition of handling
- the distribution of the efficacy variables, considering any implications for the proposed methods for statistical analysis
- a review of whether additional covariates need to be included in the analyses
- the finalization of the SAP
- The listings and tables that will be prepared for the BDRM, should include, but not be limited to:
 - Listings
 - protocol deviations
 - missing pattern and imputation method
 - outliers
 - Tables
 - Summary of the primary endpoints by study stage and underlying disease
 - Summary of conjugated bilirubin

The BDRM Report will be finalized before the blind will be broken. Formal records shall be kept of when the statistical analysis plan was finalized as well as when the blind was subsequently broken.

Statistical Analysis Plan

FK Study Identifier: SMOF-018-CP3

5 STUDY VARIABLES

5.1 Primary Variable(s)

The primary study variable is the binary occurrence of conjugated bilirubin level > 2 mg/dL during the first 28 days of study treatment, confirmed by a second sample collected 7 days after the first sample.

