Study Day	Patients < 1500 g	Patients ≥ 1500 g
Day 1	1.0 g/kg/day	2.0 g/kg/day
Day 2	2.0 g/kg/day	3.0 g/kg/day
Day 3+	3.0 g/kg/day	3.0 g/kg/day

Investigational or control drug will be infused over 20 - 24 hours, as per hospital policy, at a weight based infusion rate. If the blood draw is from the PN/lipid infusion line, then lipid (study drug) should be held for 4 hours prior to the time of blood sampling. During study treatment, serum triglycerides (TGs) will be monitored to adjust lipid dose keeping TG levels < 250 mg/dL.

Blood samples for TG monitoring will be collected as follows:

Patients < 1500 g: At 1 g, 2 g and first dose of 3 g/kg/day

Patients ≥ 1500 g: At first dose of 3 g/kg/day

Once the target dose has been reached TGs will be assessed on a weekly basis.

Should TGs exceed 250 mg/dL, lipids will be paused until analysis of another blood sample on the following morning. If TGs are below 250 mg/dL lipids are restarted. If not this procedure has to be repeated the next morning.

Dosage of other PN components:

In addition to the study drug other macronutrients will be administered at a targeted dose as follows:

- Amino acids: 2 to 4 g/kg/day
- Dextrose: 8 to 18 mg/kg/min
- Trace elements, electrolytes, vitamins will be considered according to hospital practice and applicable guidelines.
- Use and dose of heparin and carnitine have to be documented in the concomitant mediation section in the CRF.

Route of Administration: The lipid emulsions will be infused into a central or peripheral vein

Treatment: Treatment group 1: Smoflipid 20% (investigational drug)

Clinical Study Protocol SMOF-018-CP3 Smoflipid 20% lipid injectable emulsion

Treatment group 2: Intralipid 20% (control drug)

Intravenous lipid dose management

Conjugated bilirubin levels in plasma will be assessed on a weekly basis during the initial treatment phase (visits Day 1 – Day 29) and then bi-weekly in the treatment extension phase (visits Day 36 - Day 85). If in the treatment extension phase conjugated bilirubin levels increase beyond 1.5 mg/dL, then conjugated bilirubin will be assessed weekly.

- **Lipid minimization:**

If at any point conjugated bilirubin exceeds 1.5 mg/dL (> 1.5 mg/dL), lipid dose has to be decreased to 1 g/kg/day immediately; dextrose dose should be increased accordingly to maintain adequate energy provision. Lipid dose will be maintained at 1 g/kg/d and not be increased again even if conjugated bilirubin levels decrease again below 1.5 mg/dL.

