During treatment the following data must be documented daily: study drug administered, dextrose administered, amino acids administered, EN administered, body weight, AEs and concomitant medication.

During the first 28 days of treatment (initial treatment phase) physical examination findings, vital signs, body length, head circumference, conjugated bilirubin and results of biochemistry, hematology and coagulation analyses must be recorded weekly. If, at the end of the initial 28 days of treatment, PN is still indicated, patients may continue to receive the study drug until Day 84 (study extension phase).

On Day 29 the following criteria will be assessed: AEs, concomitant medications, physical examination findings, vital signs, body weight, body length, head circumference, conjugated bilirubin, results of biochemistry, hematology and coagulation analyses, α -tocopherol, sterols and fatty acids.

In the study extension phase physical examination findings, vital signs, body height, and head circumference must be recorded weekly. A blood sample for conjugated bilirubin, biochemistry, hematology and coagulation analyses will be collected every other week. However, should conjugated bilirubin exceed 1.5 mg/dL, it must be assessed weekly until conjugated bilirubin is again \leq 1.5 mg/dL. On Day 57 and Day 85, an additional blood sample will be collected for the determination of sterols, α -tocopherol and fatty acids.

Whenever a patient receives his/her last dose of study medication, an End-of-Treatment Visit will be performed the following day. The assessments for the End-of-Treatment Visit are the same as for the Day 29 Visit. If administration of IV lipids is required after the End-of-Treatment Visit, the standard lipid emulsion used in the daily routine at the respective participating site will be used.

A Follow-Up Visit must be performed 7 days after the End of Treatment Visit. At the Follow-Up Visit, all information regarding AEs and concomitant medications since the last study medication dose will be documented, and physical examination findings, vital signs, body

Clinical Study Protocol SMOF-018-CP3 Smoflipid 20% lipid injectable emulsion

weight, body length, and head circumference must be recorded. In addition, length-of-stay in the hospital will be recorded.

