12.2.5 Day 29, Day 85, and End-of-Treatment Visit

The same procedures have to be performed on Day 29 (end of initial treatment phase), Day 85 (end of treatment extension phase), and the first day after receipt of the last dose of study medication (End-of-Treatment Visit), independent of the reason for which the study medication was stopped.

Conditions for continuing in the study after Day 29 / End-of-Treatment Visit:

Patients may continue in the study after the Day 29 / End-of-Treatment Visit if:

- PN is still indicated,
and/or
- Conjugated bilirubin $> 1.5 \text{ mg/dL}$

If the patient will continue to receive PN into the study extension phase (after Day 28) and later

Clinical Study Protocol SMOF-018-CP3

Smoflipid 20% lipid injectable emulsion

weaned from study medication with a conjugated bilirubin value ≤ 1.5 mg/dL, then the End-of-Treatment Visit must be performed on the first day after receipt of the last dose of study medication.

If the patient has been weaned from study medication with a conjugated bilirubin value > 1.5 mg/dL, the patient needs to complete the End-of-Treatment Visit on the first day after receipt of the last dose of study medication, but will continue to be followed up until conjugated bilirubin levels are ≤ 1.5 mg/dL. Conjugated bilirubin levels must be assessed weekly until they are ≤ 1.5 mg/dL. As the patient will receive no study medication after the End-of-Study Visit, no additional evaluations will be performed.

If consent is withdrawn, the parent(s) or guardian(s) of the patient should be encouraged to allow the patient to complete scheduled evaluations, including the End-of-Treatment Visit evaluations and the Follow-Up Visit, and informed that the patient will be given appropriate care under medical supervision until any ongoing AEs resolve or until the patient's condition becomes stable.

No patient will receive study medication beyond Day 84 of the study.

The following procedures will be performed

- Recording of physical examination and body measurements
 - physical inspection
 - body weight
 - body length measured by a length board
 - head circumference
- Recording of vital signs
 - blood pressure
 - heart rate
 - body temperature
- Collection of a blood sample for local laboratory analysis of the following parameters:
 - Biochemistry: total bilirubin, AST, ALT, GGT, ALP, TGs, Cr, glucose, CRP
 - Hematology: CBC, leukocytes, platelets, erythrocytes, hemoglobin, hematocrit
 - Coagulation: INR

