7.10 Handling of Missing Data and Outliers

Missing data imputation is planned for both intention-to-treat and per protocol analysis. The distribution of missing value pattern, the appropriateness of imputation rules as well as the potential introduction of bias will be investigated at the BDRM. Also, the impact and handling of outliers will be discussed at the BDRM.

The following table shows the anticipated missing data patterns and the pre-specified imputation approach for the primary endpoint:

Statistical Analysis Plan

FK Study Identifier: SMOF-018-CP3

Missing Data Patterns and Imputation Approach for the Primary Endpoint

Missing Data Pattern of Conjugated Bilirubin	Imputation Approach for Primary Endpoint
A) Some missing value(s) and at least one value > 2mg/dL	
1. Value > 2mg/dL is confirmed	Primary endpoint met.
2. Value > 2mg/dL but not confirmed due to missing value	Primary endpoint met.
B) Some missing value(s) and all non-missing value(s) are <= 2mg/dL	
3. Value available on D28	Primary endpoint not met.
4. Latest value available on D22	Primary endpoint met if value > 1.5 mg/dL on D22. Otherwise, the primary endpoint will not be considered met.
5. Latest value available on D15	Primary endpoint not met if latest value <=1.5 mg/dL. Otherwise, imputation will depend on - Reason for dropout or missing data (adverse event/withdrew consent/weaned off before D28/lost to follow-up/death) - Conjugated bilirubin level(s) and trend
6. Latest value available only before D15 or no data available	Primary endpoint not met if latest value <=1.5 mg/dL. Otherwise, imputation will depend on - Reason for dropout or missing data (adverse event/withdrew consent/weaned off before D28/lost to follow-up/death) - Conjugated bilirubin level(s) and trend
C) All values missing	Primary endpoint not met.

In particular, for cases A2, B3, B4, and C information on missing conjugated bilirubin values (e.g. timing) and conjugated bilirubin levels over time as well as the reason for dropout or missing data will be reviewed for each patient during the BDRM and an individual decision for imputation will be taken.

Statistical Analysis Plan

FK Study Identifier: SMOF-018-CP3

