8.6 Treatment Exposure and Compliance

The duration of exposure (days) to a study drug, total amount of study drug administered and average daily dosage of study drug (per kg body weight) administrated will be summarized with descriptive statistics by underlying disease and treatment arm. For patients with conjugated bilirubin levels > 2 mg/dL, the cumulative dose administrated before the primary endpoint is reached (bilirubin >2 mg/dL) will be summarized by underlying disease and treatment arm.

Duration of exposure will be calculated as the difference between the date of last infusion of a study drug and the date of first infusion with a study drug plus 1 day. A data listing for treatment exposure will be included.

The duration, dose, and type of pre-treatment will be extracted from prior and concomitant medication form and summarized with descriptive statistics by underlying disease and treatment group. The frequency and percentage of patients who received PN for pre-treatment will be summarized by treatment group.

Compliance will be assessed by

- the ratio of the actual number of study drug infusions over the expected number of study drug infusions expressed as percent
- the ratio of the actual cumulative dose over the expected cumulative dose

evaluated separately over the initial and extension phase, resp., and summarized descriptively by treatment group and study phase.

Infusion of study drug will be expected on a given Study Day over the treatment period (Day 1 to Day 28 for initial treatment phase and Day 29 to Day 85 for treatment extension phase). Treatment with a study drug on a given Study Day will be considered an actual study drug infusion, provided any interruption of study drug infusion does not exceed 4 hours. Any interruption of the infusion of study drug longer than 4 hours will be documented and explained in the eCRF.

Compliance data will be provided in a data listing by patient.

Dose interruption (dose delay and modification) will be summarized with descriptive statistics (frequency and percentage) by treatment group.

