8.10 Analysis of the Primary Endpoint

The primary study variable is the number of patients in each treatment group with conjugated bilirubin levels > 2 mg/dL during the first 28 days of study treatment, confirmed by a second sample collected 7 days after the first sample.

Statistical Analysis Plan

FK Study Identifier: SMOF-018-CP3

Number and incidence of patients with conjugated bilirubin levels > 2 mg/dL during the first 28 days of study treatment will be presented overall and stratified by the patients' underlying disease (No NEC / NEC) for each stage of the study and the combined stages. Differences between treatment groups will be quantified using the estimates of the common relative risk (Mantel-Haenszel estimate) - controlling for stratum - and the Cochran-Mantel-Haenszel statistics of general association for the combined strata, and corresponding 95% confidence intervals will be presented.

Data from each stage without imputation will be summarized with descriptive statistics, combined data from both stages with and without imputation will be summarized with descriptive statistics using the ITT analysis set and the per protocol set.

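### Does the primary endpoint need a named closing sample and a stated tolerance for the seven-day confirmation?

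*SAP*

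**What the plan says.** SAP 5.1 defines the endpoint: "The primary study variable is the binary occurrence of conjugated bilirubin level > 2 mg/dL during the first 28 days of study treatment", to be confirmed by a second sample a week after the first. SAP 8.10 repeats the window without naming its last draw: "Number and incidence of patients with conjugated bilirubin levels > 2 mg/dL during the first 28 days of study treatment".

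The imputation table in SAP 7.10 has two rows that bear on this. Row B3 reads "Value available on D28" and gives the endpoint as not met. Row A2 reads "Value > 2mg/dL but not confirmed due to missing value" and gives it as met. Both rows are also listed for individual decision at the blinded data review.

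The schedule (protocol Section 2, SAP 4.1) has draws on Days 8, 15 and 22 (±1 day), on Day 29 / End of Treatment (+1 day), and at Follow-up seven days after End of Treatment (±1 day). Day 36 and later visits carry ±2 days. Footnotes b and c require weekly sampling, or a Follow-up sample, once conjugated bilirubin is above 1.5 mg/dL. Protocol 12.2.4 instead gives ±1 day for all treatment visits.

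**The concern.** A programmer working from SAP 5.1 and 8.10 alone has to infer which visit closes the primary endpoint window. SAP 7.9 counts the first infusion as Study Day 1, so 28 days means Study Days 1 to 28, and the Day 29 draw lies just outside. SAP 8.6 seems to support that boundary: "Day 1 to Day 28 for initial treatment phase and Day 29 to Day 85 for treatment extension phase".

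The stake would not be trivial if the Day 29 draw were dropped. Protocol 7.2 cites a report on surgical neonates with a median time to cholestasis of 23 days and 77% of cases within five weeks. A straight line between those points (an assumption, and on a scale of days of parenteral nutrition rather than study days) gives 0.50 + 0.27 × 6/12 = 0.635 by day 29. The share of those cases arising after day 23 is then 0.135/0.635, or about 21%.

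The confirmation rule also has no written tolerance. Visits may move within their windows, so consecutive draws need not be exactly seven days apart. A second value at or below 2 mg/dL taken off the nominal day might be read as a failed confirmation (not met) or as a missing one (row A2, met), which are opposite results.

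**Working it through.** The plan gives no figure on this point, so the check is a comparison of passages and of days.

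**1. Which draw closes the window**

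Allowed study days from the schedule: Day 8 visit, 7–9; Day 15, 14–16; Day 22, 21–23; Day 29, 29–30; Day 36, 34–38 (or 35–37 under protocol 12.2.4). Study Day 28 lies in none of them, so D28 is not a scheduled visit.

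- Protocol 7.1 equates the two periods: "During the first 28 days of treatment (initial treatment phase".
- Protocol Section 1 places bilirubin sampling "on a weekly basis during the initial treatment phase (visits Day 1 – Day 29".
- Protocol 12.2.5 has "The same procedures have to be performed on Day 29 (end of initial treatment phase".
- Footnote a of the schedule puts the End-of-Treatment visit on the day after the last dose. Dosing on Days 1–28 is therefore closed by the Day 29 draw.
- In SAP 7.10, rows B3, B4 and B5 step back through D28, D22 and D15. If Day 29 did not count, B3 would have no scheduled draw to refer to. B4 would impute a result for a patient whose Day 22 draw was already the last one that mattered. The rows work only if D28 means the Day 29 visit.
- The sentence in SAP 8.6 counts expected infusions for compliance. Day 28 as the last initial-phase infusion and Day 29 as the closing assessment are compatible.

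No passage states a cut at Study Day 28.

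**2. The seven-day confirmation**

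If each visit moves freely in its window, the gap runs from (earliest second day − latest first day) to (latest second day − earliest first day):

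| Pair | Gap in days |
|---|---|
| Day 8 to 15 | 14−9 = 5 to 16−7 = 9 |
| Day 15 to 22 | 21−16 = 5 to 23−14 = 9 |
| Day 22 to 29 | 29−23 = 6 to 30−21 = 9 |
| Day 29 to 36 (±2) | 34−30 = 4 to 38−29 = 9 |
| Day 29 to 36 (±1) | 35−30 = 5 to 37−29 = 8 |
| End of Treatment to Follow-up | 6 to 8 |

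With visits spread evenly and independently, 3 of 9 pairs are exactly seven days apart for Day 8 to 15, and 2 of 10 for Day 29 to 36 (±2). That suggests 67% to 80% of pairs miss seven days. Independence is the wrong model here, however. Protocol Section 1 (early discontinuation) and 10.4 time the confirming draw from the first high value. Adding exactly seven days to each allowed start day gives:

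| First draw on day | Plus 7 | Next window | In window? |
|---|---|---|---|
| 7–9 | 14–16 | 14–16 | all |
| 14–16 | 21–23 | 21–23 | all |
| 21–23 | 28–30 | 29–30 | all but 21 → 28 |
| 29–30 | 36–37 | 34–38 or 35–37 | all, under either window |
| End of Treatment | +7 | Follow-up, +6 to +8 | yes |

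Of the 11 numbered start days, 10 allow an exact seven-day confirmation within the next window. The two versions of the Day 36 window make no difference to this result.

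**3. A second value outside the interval**

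Row A2 applies when confirmation fails because a value is missing. A second sample that exists and is at or below 2 mg/dL is not missing, so in plain words the first value was not confirmed. Edge cases in A2 and B3 go to individual blinded review. SAP 6 asks that decisions stay consistent with those taken before the interim analysis.

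**The case for a change.** The strongest reply is that blinded review does not cover every output. It settles imputation, but SAP 8.10 also calls for summaries without imputation, for each stage and for both combined. There row A2 does not operate, and the confirmation rule alone fixes the numerator. SAP 8.12.1.2 uses the same seven-day wording for the time-to-event variable and has no imputation table. A relative risk with a 95% confidence interval is still reported, and readers may fairly expect to reproduce it from the SAP text.

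This stands as a remark on completeness: the tolerance is not written down in either document. It does not show that any patient would be misclassified. Protocol 11.3 describes the confirming draw as the next weekly one, which is what an analyst would take. Footnotes b and c ensure that such a draw is scheduled even after a high Day 29 or End-of-Treatment value. The interim analysis, which included 152 randomised patients, had its own Interim Analysis Plan. That plan is not among the documents reviewed and may hold the rule. A new tolerance written after an unblinded interim could also depart from the interim derivation, and allowing any draw within the visit windows would admit gaps of 4 to 9 days in place of the stated seven.

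**Conclusion.** No change to the plan follows. D28 is a clerical slip for the Day 29 / End-of-Treatment draw, and with that draw counted no event is gained or lost. The missing tolerance is a detail that analysts can fill from the schedule and protocol 11.3. The documents give no basis for counting misclassified patients, and none is shown. SAP 4.5 and 7 rule out hypothesis tests and p-values, so no decision rule depends on the point.

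This rests on three readings: D28 means the Day 29 visit; confirming draws are timed from the first high value; and an available second value at or below 2 mg/dL is not a missing value. The first is an inference, but the imputation rows make sense under no other. Separately, protocol 12.2.4 (±1 day) and the schedule (±2 days from Day 36) contradict each other and must be reconciled as housekeeping. SAP 7.11 already takes the schedule's windows for analysis, and a confirming draw exactly seven days after the Day 29 visit fits both.
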